### **Exclusion Criteria**

Patients with incomplete data and no commitment to follow up visits

Presence of the following ocular conditions preoperatively: unstable refraction, severe ocular surface disease, cataract, glaucoma, corneal pathology such as Fuch's dystrophy or corneal scarring, uncontrolled intraocular inflammation, macular scarring or any other retinal issue that may adversely affect vision after surgery.

## **3.4 Identification and Recruitment of Participants**

Potential participants will be identified by screening of all medical records from the above hospital regardless of the time of the surgery.

Study investigators will identify study participants individually after screening of medical records.

Since this study is retrospective, initial surgery consent was considered as the participant consent for the study.

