### 3.3 Study Population

All refractive surgery candidates attending the above hospital for the purpose of phakic introcular lens implantation were included in the study. However, the initial group allocation occurred before the commencement of the study on the basis of surgeon and patient preference, thereby, randomization was on convenient basis.

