### **Inclusion Criteria**

Refractive surgery candidates

Aged from 18-55 years

Phakic intraocular lens implantation was performed (ICL type)

Committing to at least one preoperative visit for baseline assessment and multiple postoperative visits (at least 2 visits within a year) for follow-up assessment.

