## **3.5 Study Interventions / Procedures**

After enrolment, the record of each participant is examined meticulously for completeness of preoperative and postoperative data pertaining to study including:

Patient age and gender, date of the procedure and its operative notes including laterality and surgical steps.

preoperative and postoperative assessments such as uncorrected and best corrected visual acuity, refractive error quantification both objectively utilizing an autorefractometer autorefractor Nidek ARK 1 (Nidek Inc, Gamagori, Japan) and subjectively as manifest refraction, clinical slit-lamp examination notes, intraocular pressure with air puff tonometers, AC depth assessment by Pentacam Scheimpflug (Oculus Optikgeräte GmbH Inc., Wetzlar, Germany), specular microscopy study of corneal endothelial cells (endothelial cell density (ECD), coefficient of variation (CV) and hexagonality) using Topcon SP-1p Specular Microscope (Topcon Corporation, Tokyo, Japan),

Typically, there is a preoperative visit and multiple postoperative visits extending over the period of 1-2 years after the procedure.

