## 2- Reduced OVD group

In this group of patients, the ICL was implanted with the use of cohesive OVD only.

There is one primary outcome of interest which is the unaided visual acuity after the surgery, and several secondary outcomes including postoperative intraocular pressure, corneal specular microscopy parameters (ECD, CV and hexagonality), and the observed adverse events that can happen during the operation or postoperatively.

Data will then be stored electronically in a sheet format to enable for later statistical analysis.

Data collection was started at the conduct of the study in March 2024, and it is expected to be completed 3-4 months later.

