## 6 Study Impact and Significance

Traditionally dispersive OVDs has been used extensively during loading and implantation steps of ICL surgery. Reducing both the amount and the types of viscoelastics used (cohesive only) might potentially reduce cost and time of the procedure and might provide a substitute for safety studies regarding omitting or further reduction of cohesive OVDs and utilizing BSS only which carries lower risk of raised IOP and lower cost of the procedure.

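### With no calendar window, common follow-up horizon or outcome time points, technique can be mixed with surgery era and length of follow-up, and the unadjusted comparison would not correct it

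*Combined protocol and SAP*

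**What the plan says.** Four parts of the combined protocol and SAP bear on this.

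- **Calendar window.** Section 3.4: "Potential participants will be identified by screening of all medical records from the above hospital regardless of the time of the surgery". The only other calendar information is in section 3.6: data collection began in March 2024 and "it is expected to be completed 3-4 months later". No first or last surgery date is set.
- **Follow-up.** The inclusion criteria ask for "multiple postoperative visits (at least 2 visits within a year) for follow-up assessment". This is a floor, with no fixed visit times. Section 3.5 adds a description, not a requirement: "Typically, there is a preoperative visit and multiple postoperative visits extending over the period of 1-2 years after the procedure".
- **Outcomes.** Section 3.6 names unaided visual acuity as primary, and intraocular pressure, endothelial parameters and adverse events as secondary. None has a time point, and adverse events cover any occurrence during or after the operation.
- **Groups and analysis.** Under section 3.3, "the initial group allocation occurred before the commencement of the study on the basis of surgeon and patient preference". Section 4.2 plans chi-squared, unpaired t or Mann-Whitney tests between groups. It includes no covariates, no person-time and no time-to-event method. It does compare the groups on every item collected under section 3.5, and those items include surgery date: "Patient age and gender, date of the procedure and its operative notes including laterality and surgical steps".

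**The concern.** The aim in section 2 is to learn whether leaving out the dispersive OVD is safe and suitable. A crude count of harms answers that only if both groups were watched for similar lengths of time and operated on under similar conditions. The plan secures neither.

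The protocol treats the two-OVD technique as the established one. Section 2 calls it standard, section 1 speaks of modifying it, and section 6 says "Traditionally dispersive OVDs has been used extensively during loading and implantation steps of ICL surgery". If practice at this hospital moved from one technique to the other, the reduced-OVD cases would tend to be the later ones. Two separate problems would follow.

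- **Follow-up length.** Later cases would have had less time for slow harms to appear before the records were read. Section 1 itself names cataract as a complication, and endothelial change also accumulates. Fewer recorded late harms could then reflect shorter observation.
- **Era.** Anything else that changed over the years, such as surgical experience, equipment or patient selection, would differ between the groups. The sign is unknown: general improvement would favour later cases, while a learning curve with a modified technique would work against them.

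The absence of time points also reaches the primary outcome, because visual acuity read at different intervals after surgery is not the same measurement in the two groups.

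**Working it through.** The plan states no sample size, event rate or follow-up by group, so it has no figure of its own to reproduce. The calculation below is an illustration.

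**Inputs from the plan.** Follow-up typically spans 1 to 2 years (section 3.5). Harms are compared as crude percentages (section 4.2).

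**Assumed inputs, not in the documents.** Late harms occur at a constant hazard h of 1%, 2% or 5% per year, the same in both groups. The traditional group is followed for 2 years and the reduced-OVD group for 2, 1.5 or 1 year.

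**Formula.** Crude risk = 1 − exp(−h × t). Crude risk ratio = reduced-OVD risk ÷ traditional risk. The true ratio is 1.

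| h per year | Risk at 2 y | Risk at 1.5 y | Risk at 1 y | Ratio, 2 vs 2 y | Ratio, 2 vs 1.5 y | Ratio, 2 vs 1 y |
|---|---|---|---|---|---|---|
| 1% | 1.98% | 1.49% | 1.00% | 1.00 | 0.75 | 0.50 |
| 2% | 3.92% | 2.96% | 1.98% | 1.00 | 0.75 | 0.51 |
| 5% | 9.52% | 7.23% | 4.88% | 1.00 | 0.76 | 0.51 |

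At h = 2%, for example, 1 − exp(−0.04) = 3.92% and 1 − exp(−0.02) = 1.98%, and 1.98 ÷ 3.92 = 0.51.

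The assumed hazard hardly matters. When h × t is small, the crude ratio is close to the ratio of follow-up times (1 ÷ 2 = 0.5; 1.5 ÷ 2 = 0.75).

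The same mechanism can hide a real harm. If the reduced-OVD hazard were truly twice as high (2h) but follow-up were 1 year against 2, both risks would equal 1 − exp(−2h) and the crude ratio would be 1.00.

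**Limits of the illustration.** It applies to late, accumulating events. It does not apply to intraoperative events or to the early pressure rise that section 1 links to retained viscoelastic, since both fall within even short follow-up. Endothelial density is a mean and not a risk, so the ratios do not carry over as numbers, although readings taken at unequal times have the same problem. The size of any era effect cannot be computed from the documents.

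**The case against.** The strongest reply is that nothing in the documents dates either technique at this hospital. Allocation by preference (section 3.3) fits a period in which both were on offer, and the remark about traditional use in section 6 concerns ICL surgery in general. If both techniques were used evenly over the same dates, there is no era difference and no systematic follow-up difference. This stands, and it is why the point is conditional.

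Section 4.2, read literally, also compares surgery date between the groups, so an imbalance might be seen. That stands in part. Length of follow-up is not a listed item, and seeing an imbalance does not correct it.

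A reader might go further in three ways that the documents do not support.

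- **That the reduced-OVD group is the newer one and technique is in fact confounded with era.** This is an inference from wording alone.
- **That both mechanisms flatter the new technique.** Only shorter follow-up has a predictable direction.
- **That the distortion could reach a ratio near 0.25.** This would need about half a year of follow-up across the whole reduced-OVD group against 2 years in the other. The inclusion rule allows this for individual patients, but it is below the typical 1-2 years in section 3.5.

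Finally, adverse events are secondary. The calculation says nothing about the size of any effect on visual acuity, the primary outcome.

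**Conclusion.** The point holds as a conditional weakness of design and analysis. The text establishes four gaps: no calendar window, a follow-up minimum without a common horizon, no outcome time points, and no adjustment for date or follow-up. Whether these produce bias depends on surgery dates and follow-up by group, which the plan does not give.

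If reduced-OVD cases are on average more recent, late harms in that group would be under-counted. Follow-up of 2 versus 1 year gives an apparent risk ratio of about 0.5 with no true difference, and 2 versus 1.5 years about 0.75. With equal follow-up the bias is nil. These figures assume a constant, equal hazard of 1-5% per year and follow-up within the range the plan calls typical. Any era effect has unknown size and sign.

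The change is worth making because the question is one of safety, the plan has no step that would correct the problem, and the remedy draws on records already being extracted.

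**What to change.** **Sections 3.6 and 4.2, outcomes.** Give each outcome a prespecified postoperative window, the same in both groups, chosen from the hospital's usual visit pattern before outcomes are compared. Read visual acuity, pressure and endothelial parameters in that window.

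**Section 4.2, adverse events.** Count them only up to the same follow-up limit in both groups, or report late events as rates per person-year to the last recorded visit. The person-year form also deals with patients whose last visit falls before the limit. Keep intraoperative and early events as simple proportions, because dividing them by person-time would distort them.

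**Section 4.2, reporting.** Extend the planned comparison of section 3.5 items to show the distribution of surgery dates and of follow-up length by group.

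**Section 4.2, adjustment.** Add a regression of each main outcome on technique with surgery date as a covariate. This is a new analysis, since the plan currently has only two-group tests. Where the techniques overlap in calendar time, add a sensitivity analysis restricted to that period. If the overlap is small or empty, say so, because regression cannot then separate technique from era.

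A cut-off for the last eligible surgery date would not be enough by itself. A patient with two early visits would still qualify and still have short observed follow-up.

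**Cost.** New wording and some extra analysis. Surgery date is already collected; the last-visit date must be taken from the same records. Records without a visit in the common window leave that comparison, and their number should be reported by group. Section 3.7 should say that they leave that comparison only and not the whole study.

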## **3.5 Study Interventions / Procedures**

After enrolment, the record of each participant is examined meticulously for completeness of preoperative and postoperative data pertaining to study including:

Patient age and gender, date of the procedure and its operative notes including laterality and surgical steps.

preoperative and postoperative assessments such as uncorrected and best corrected visual acuity, refractive error quantification both objectively utilizing an autorefractometer autorefractor Nidek ARK 1 (Nidek Inc, Gamagori, Japan) and subjectively as manifest refraction, clinical slit-lamp examination notes, intraocular pressure with air puff tonometers, AC depth assessment by Pentacam Scheimpflug (Oculus Optikgeräte GmbH Inc., Wetzlar, Germany), specular microscopy study of corneal endothelial cells (endothelial cell density (ECD), coefficient of variation (CV) and hexagonality) using Topcon SP-1p Specular Microscope (Topcon Corporation, Tokyo, Japan),

Typically, there is a preoperative visit and multiple postoperative visits extending over the period of 1-2 years after the procedure.

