## **3.6 Data collection and analysis**

Data will be collected by study co-investigators with assistance from IT personnel at the respective hospital from patients records that were identified as eligible for the study according to the inclusion criteria above. According to their data, participants will be split into two groups:

1- Traditional OVD group

In this group of patients, the ICL was implanted utilizing both cohesive and dispersive ophthalmic viscosurgical device.

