### 4.2 Statistical methods

After collection of data from patients records and its subjection to thorough analysis for incompleteness and exclusion criteria, these data will be stored electronically in sheet formats for later analysis. All statistical test and subsequent analyses will be performed using SPSS version 26 (IBM statistical software). Data will be classified into categorical and numerical. Categorical variables were described using frequencies and percentages and were analysed using Chi-squared test. Numerical variables, described as mean  $\pm$  standard deviation, will be subjected to tests of normality to determine the appropriate statistical tests for inter- and intra-group comparisons. Unpaired t test or Mann-Whitney test was used to compare the two groups (traditional and modified OVD) according to fulfilled statistical assumptions. These two groups were compared for statistically significant difference regarding all parameters that were collected as per section 3.5 of this protocol. These statistical comparisons were made both preoperatively to determine baseline characteristics of the study participants and postoperatively to determine any significant difference between the two groups. Within the same group whether traditional or reduced OVD, all of the aforementioned parameters were compared again pre- and postoperatively this time using either one sample paired t test or Wilcoxon signed-rank test according to fulfilled statistical assumptions. Significance was considered at P value less than 0.05.

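### Technique followed surgeon and patient preference, but surgeon is neither named for extraction nor used in any planned analysis, so a surgeon difference could be reported as an OVD effect

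*Combined protocol and SAP*

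**What the plan says.** Section 3.3 describes how patients came to be in one group or the other: "the initial group allocation occurred before the commencement of the study on the basis of surgeon and patient preference". The surgeon is therefore one of two stated determinants of technique.

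Section 3.5 opens its extraction list by checking each record for "completeness of preoperative and postoperative data pertaining to study including" a set of items. The first of these are "Patient age and gender, date of the procedure and its operative notes including laterality and surgical steps"; the rest are visual, refractive, pressure, anterior chamber and endothelial measurements. The operating surgeon is not named.

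Section 3.6 forms the groups: "According to their data, participants will be split into two groups". It names unaided visual acuity as the primary outcome. Intraocular pressure, the specular parameters and adverse events are secondary.

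Section 4.2 gives the between-group analysis: "Unpaired t test or Mann-Whitney test was used to compare the two groups (traditional and modified OVD) according to fulfilled statistical assumptions", with a Chi-squared test for categorical variables. The variables compared, at baseline and after surgery, are those collected under section 3.5. No covariate model, matching, stratification or clustering term appears anywhere.

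**The concern.** The protocol itself says that surgeon preference helped decide who received which technique. If surgeons also differ in their results, surgeon is a confounder of the OVD comparison. The Background (section 1) supplies a mechanism: it links incomplete viscoelastic removal to early pressure rise, and extra manipulation to cataract. Both plausibly vary with the operator, and both bear on the study's question of whether the reduced-OVD technique is safe.

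This is distinct from patient case mix. Adjusting for every patient variable in section 3.5 would leave surgeon out. Because the baseline comparison is confined to section 3.5 items, an imbalance in surgeons would not be displayed either. A finding for or against the reduced-OVD technique could then partly be a finding about surgeons. The shift can go in either direction, so it could create a difference or hide one.

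**Working it through.** The plan has no figure to reproduce: section 4.1 gives no sample size, power, effect size or standard deviation. The check has two parts.

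**Reading the sections together.** Section 3.3 makes surgeon preference a cause of group membership. Section 3.5 does not name surgeon for collection. Section 4.2 compares groups only on section 3.5 items and without adjustment. Followed as written, the plan has no step at which a surgeon difference would be seen or removed.

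**Illustrating the size.** From the documents: significance at 0.05 (section 4.2). Assumed, because the documents do not say: a two-sided test; no true OVD effect; two surgeons, A and B, whose mean outcomes differ by d standard deviations; n independent observations per group; surgeon A's share of cases is p1 in one group and p2 in the other.

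- Spurious shift between groups, in SD: s = d × (p1 − p2)
- Standard error of the difference, in SD: SE = √(2/n)
- Chance of P < 0.05 = Φ(s/SE − 1.96) + Φ(−s/SE − 1.96)

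For n = 50, SE = √(2/50) = 0.20. With d = 0.3:

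- Shares 60/40 versus 40/60: s = 0.3 × 0.2 = 0.06 and s/SE = 0.3. Chance = Φ(−1.66) + Φ(−2.26) = 0.048 + 0.012 = 0.060.
- Shares 80/20 versus 20/80: s = 0.3 × 0.6 = 0.18 and s/SE = 0.9. Chance = Φ(−1.06) + Φ(−2.86) = 0.145 + 0.002 = 0.147.
- Surgeon and technique coincide: s = 0.3 × 1 = 0.30 and s/SE = 1.5. Chance = Φ(−0.46) + Φ(−3.46) = 0.323 + 0.000 = 0.323.

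The same calculation over a range of assumptions:

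| n per group | d (SD) | 60/40 vs 40/60 | 80/20 vs 20/80 | coincide |
|---|---|---|---|---|
| 50 | 0.2 | 0.055 | 0.092 | 0.170 |
| 50 | 0.3 | 0.060 | 0.147 | 0.323 |
| 50 | 0.5 | 0.079 | 0.323 | 0.705 |
| 100 | 0.2 | 0.059 | 0.136 | 0.293 |
| 100 | 0.3 | 0.071 | 0.247 | 0.564 |
| 100 | 0.5 | 0.109 | 0.564 | 0.942 |

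With one surgeon, or equal shares in the two groups, s = 0 and the chance stays at 0.05. For a given imbalance, a larger sample makes the problem worse, because the shift stays fixed while the standard error shrinks.

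**The case against.** The strongest reply is that the documents do not show that more than one surgeon operated. Section 3.2 names one private hospital, and section 3.3 speaks of surgeon preference without a number. One surgeon choosing case by case would fit the text, and there would then be no surgeon shift. Patient preference also played a part, which makes overlap within surgeon more likely. This stands, and it makes the concern conditional. It does not remove it, because nothing in the plan would reveal which situation applies.

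A second reply is that surgeon may be recoverable: the section 3.5 list is introduced as non-exhaustive and takes in the operative notes. This also stands. A claim that surgeon will be absent from the data would go too far. The firmer gap is that no analysis uses it.

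Two stronger readings are tempting, and the documents do not support either.

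- A reader might infer that each surgeon used one technique, and that the tests are therefore badly anti-conservative. With complete nesting, the design effect 1 + (m − 1) × ICC does give large figures. For m = 50 cases per surgeon, an ICC of 0.01 gives 1.49 and an error rate of 10.8%; an ICC of 0.05 gives 3.45 and 29.1%. But nesting is stated nowhere, and the 60/40 case above is close to nominal.
- A reader might infer that eyes are tested as independent, so that P values are too small. Section 4.2 never mentions eyes, and section 3.6 groups participants and patients; the unit of analysis is simply unstated. The direction is not fixed either. If both eyes of every patient are entered with the same technique, a between-eye correlation of 0.3 (design effect 1.3) gives an error rate of 0.086. If fellow eyes received different techniques, the same correlation (design effect 0.7) gives 0.019, so P values would be too large.

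**Conclusion.** The concern holds in conditional form. Surgeon preference is a stated determinant of technique, surgeon is not named for extraction, and no planned analysis uses it. If more than one surgeon operated and their use of the techniques differed, the planned tests could report a surgeon difference as an OVD effect.

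The size cannot be fixed from the documents. On the central assumptions (0.3 SD between two surgeons, 50 independent observations per group, no OVD effect), the chance of a significant result rises from the nominal 5% to about 6%, 15% or 32% as the imbalance grows. It stays at 5% with a single surgeon. The documents do not establish complete nesting, eyes as the unit of analysis, or P values that are always too small.

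**What to change.** 1. Record a coded operating surgeon from the operative notes. Exempt this item from section 3.7, which removes any participant missing a section 3.5 item, and code it as unknown where it is not recorded. Without the exemption, adding surgeon to the list would itself cause exclusions.
2. In section 4.2, tabulate technique by surgeon before any outcome comparison.
3. Where surgeons used both techniques, make the between-group comparison within surgeon. Use a linear model with surgeon as a fixed effect for unaided visual acuity, intraocular pressure and the specular parameters; a surgeon-stratified rank test where normality fails; and a surgeon-stratified exact test for adverse events.
4. If no surgeon used both techniques, state that OVD and surgeon cannot be separated, and do not attribute the group difference to OVD. No analysis can rescue that case. If one surgeon did every case, one sentence saying so closes the point.
5. State the unit of analysis. If both eyes of a patient are entered, use one eye per patient or a model with patient as the cluster; a surgeon effect does nothing for correlation between fellow eyes.

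The cost is one coded column from notes already being read and a few sentences in section 4.2. The downside is wider confidence intervals where few surgeons used both techniques. The change deals with surgeon only. Section 3.4 sets no limit on surgery date, so technique may also follow calendar time, which a surgeon term would not necessarily remove.
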